14.2 Serious adverse events

PTSD Serious Adverse Events are defined as hospital admission for mental ill-health, self-harm, suicide and attempted or completed suicide.

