5.1 PTSD and NHS therapy for military veterans

PTSD is a psychiatric disorder resulting from experiencing or witnessing traumatic events such as threatened or actual death, serious injury or sexual violence [1]. Around 17% of combat military veterans experience PTSD; this rate may be as high as 37% in veterans living in Northern Ireland. This compares to around a 4% PTSD prevalence in the general English population [2, 3]. There are 2.4 million veterans in the UK, equating to 425,000 veterans living with PTSD [4]. People aged 70+ account for 50% of UK veterans [5]. Ethnic minority veterans make up 2.3% of the veteran population [5]. Women currently make up 13.6% of the veteran population [5] and this is expected to grow to 13% by 2028 [6]. Despite this just 2% of the veteran research mentions women and even smaller proportion focuses on women as the primary source [7]. There is only partial overlap between the traumatic events reported by female veterans and those reported by males. In particular, sexual trauma is more commonly reported by female veterans (during- and pre-military) [8]. The prevalence of PTSD is marginally higher in women veterans although the nature of the PTSD symptoms are comparable with male veterans [3, 8]. Women veterans are less likely to receive a PTSD diagnosis when sexual trauma is a causative factor [8, 9]. PTSD adversely impacts social functioning, including homelessness, physical health problems, and frequently is associated with mental health comorbidities such as substance misuse and suicidality [1, 10-12]. 80% of veterans with PTSD also have Complex-PTSD (CPTSD) resulting from multiple traumas [13]. Chronic PTSD is unlikely to resolve spontaneously, and the risks of adverse outcomes increases if untreated [14]. Current NICE recommended therapies for PTSD in veterans are Trauma-Focussed CBT (TF-CBT) and Eye Movement Desensitisation and Reprocessing (EMDR) [1, 15], although EMDR is not recommended for combat-related PTSD. Both treatments, whilst cost-effective, have important limitations. Both typically require between 8 to 18 sessions for optimal efficacy [16] and are extensive and time-consuming; resulting in limited NHS-based therapist numbers causing potentially lengthy treatment waiting lists. The trauma-focussed nature of both TF-CBT and EMDR leads to treatment dropout in research studies of up to 58% [17] while non-response treatment rates to TF-CBT in veterans can be as high as 50% [15, 18]. Given the scale of the problem of PTSD in veterans, and the practical challenges of providing timely, evidence-based therapy for PTSD, there is a pressing need for accessible, cost- and time effective treatments.

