14.1 Adverse events

PTSD Adverse Events are defined as a \geq 10 point rise in the self-report PCL-5 since the previous therapy session or a 15 point rise from baseline or the maximum score of 80 being reached and/or relapse into alcohol and/or substance misuse at a hazardous level which integrated with the clinical judgement of the treating therapist will determine the action taken.

Self-harm adverse events are defined as responding 1 or above on the PHQ-9, question 9 and

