14.3 Care escalation procedures

If the participant is in therapy, Inspire will hold responsibility and clinical governance accountability for the participant's mental health and wellbeing, including their own safety and where relevant the safety of others and including the safeguarding of children and vulnerable adults. If at point of referral or during the course of treatment, Inspire therapists become concerned about the welfare of any participant or immediate family member they will escalate their concerns through Inspire's standardised risk assessment, escalation, management and safeguarding policies and procedures. Where necessary they will contact the participant's GP to mobilise referral to crisis response, NHS primary or secondary care. Likewise, if a safeguarding and vulnerable adults concern is identified this will be escalated, acted on and reported to the relevant statutory body – safeguarding team.

Before the participant is referred to Inspire and after discharge, the participant's GP holds responsibility and accountability for the participant's mental health and wellbeing and this includes their safety. If the participant scores on the PCL-5 indicate an adverse event, the unmasked researcher responsible for participant safety will make contact with the participant within six hours of noting the rise in score and encourage them to contact their GP and/or case worker. They will advise the participant that they will need to contact the participants GP and/or case worker to alert them to the rise in PTSD symptoms. The research team will review all incoming follow-up PCL-5 and PHQ-9 scores within 72 hours of receipt.

All AE will be recorded and reported to the study PI within 72 hours and will be discussed at the biweekly research core-team sub-group meeting. A report will be included in the TSC reporting for review.

A Serious Adverse Event that occurs following discharge from Inspire but whilst in the trial will be investigated by one of the study's senior investigators (i.e. [name] or [name]) using Inspire's SAE investigational policies and procedures. The investigational report will be submitted to the DMEC chair.

The DMEC chair will be notified within 24 hours of the research team being notified of all serious adverse events.

All AE and SAE and the clinical and research team actions will be logged in the Trial Management File.

15 Ethics and regulatory approvals

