1.0 Lines of responsibility and accountability

- 1.1 Up until the point at which a participant has undertaken their eligibility confirmation assessment with King's contracted Assistant Psychologists (AP) and before their details are forwarded to Inspire on randomisation and for therapy appointments to be allocated, the participant's GP holds responsibility and accountability for the participant's mental health and wellbeing and this includes their safety.
- 1.2 For those participants randomised to receive FIRST therapy immediately (the Intervention arm) from the point at which the participant's details are handed over to Inspire to arrange their therapy sessions through to the point of discharge, Inspire have responsibility and clinical governance accountability for the participant's mental health and wellbeing and including their own safety and where relevant the safety of others and including the safeguarding of children and vulnerable adults.
- 1.3 From the point of discharge from Inspire therapy to the point of 52-week follow-up or withdrawal from the trial, the Intervention participant's GP holds responsibility and accountability for the participant's mental health and wellbeing and this includes their safety.
- 1.4 For those participants randomised to receive FIRST therapy in 20 weeks (the Control arm) up until therapy begins the participant's GP continues to hold responsibility and accountability. At the point therapy delivery with Inspire begins at 20-weeks until the point of discharge approximately four weeks' later, Inspire have responsibility and clinical governance accountability. Once therapy is completed for these participants, they are discharged from Inspire and their time in the study is complete. Responsibility for the participant's mental health and wellbeing returns to their GP.
- 1.5 Participant safety will be a standing agenda item on every fortnightly core research team sub-group meeting.
- 1.6 Data Monitoring and Ethics Committee (DMEC) will meet once during the Proof of Concept trial and four times during the full trial and comprises two trauma experts and an independent statistician. The DMEC terms of reference will operate according to the King's Clinical Trials Unit Standard Operating Procedures. The research team will report any participant safety issues to the DMEC within 48 hours of each fortnightly core research team sub-group meeting.

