6.0 Care escalation procedures in the case of serious adverse event

- **6.1** A serious Adverse Event that occurs during therapy will be investigated by Inspire according to their standardised clinical protocols and clinical governance framework.
 - 6.1.1 The serious adverse event will be investigated by Inspire's clinical lead or delegated representative using Inspire's standardised SAE procedures template and within an agreed time-frame contingent on the nature and seriousness of the event.
 - 6.1.2 The completed investigation report will include recommendations, shared learning and corrective actions each to be completed within a specified time frame, presented to and signed off by the Inspire CEO Board alongside being shared with the DMEC chair for review.
- **6.2** A Serious Adverse Event that occurs following discharge from Inspire but whilst in the trial will be investigated by one of the study senior investigators (i.e. [name] and [name]) using Inspire's SAE investigational policies and procedures. Inspire protocols and timeframes will be used. The investigational report will be submitted to the DMEC chair.

6.3 The DMEC chair will be notified within 24 hrs of the research team being notified of all serious adverse events.

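### The only SAE definition lists mental-health events, so a death of other or undetermined cause does not clearly trigger the 24-hour DMEC notice or the investigation

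*Protocol*

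**What the plan says.** Protocol 14.2 reads: "PTSD Serious Adverse Events are defined as hospital admission for mental ill-health, self-harm, suicide and attempted or completed suicide". Appendix 1 item 2.5 uses the same words.

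Two protections are tied to the SAE label:

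- **Notice.** Section 14.3 says "The DMEC chair will be notified within 24 hours of the research team being notified of all serious adverse events", and Appendix 1 item 6.3 says "The DMEC chair will be notified within 24 hrs of the research team being notified of all serious adverse events".
- **Investigation.** Appendix 1 item 6.1 says "A serious Adverse Event that occurs during therapy will be investigated by Inspire according to their standardised clinical protocols and clinical governance framework". For later events, section 14.3 says "A Serious Adverse Event that occurs following discharge from Inspire but whilst in the trial will be investigated", in that case by a senior investigator; Appendix 1 item 6.2 agrees.

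A slower and more general route also exists. Appendix 1 item 1.6 says "The research team will report any participant safety issues to the DMEC within 48 hours of each fortnightly core research team sub-group meeting", and section 14 has an equivalent sentence.

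**The concern.** An SAE is normally recognised by how serious the event is. Here it is recognised by what kind of event it is, and every kind listed is psychiatric. A fatal accident, a death from physical illness and a death whose cause is not yet known are not on the list. Neither is a life-threatening overdose or injury that nobody has identified as self-harm.

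The protocol itself expects vulnerability of this sort. Section 5.1 says that PTSD "frequently is associated with mental health comorbidities such as substance misuse and suicidality", and mentions physical health problems and homelessness in the same sentence. A sudden death whose cause is unclear when first reported is among the events that an oversight committee most needs to hear of quickly. Staff who follow the text as written would find no instruction to send it within 24 hours and no instruction to investigate it.

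**Working it through.** No sample size, power or event count is at issue. The check is a reading of every section that defines or uses adverse events, followed by two short sums.

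**Step 1: is there a wider definition anywhere?** Sections 14 to 14.3, section 15.1 and all of Appendix 1 were read for one.

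- 14.2 and Appendix 1 item 2.5 carry the identical list. It is introduced as a definition, with no wording to mark the items as examples and no criterion of seriousness.
- Death enters the list only as completed suicide. No section names death from any cause, a life-threatening event, or admission for a non-psychiatric reason.
- The sentence can be parsed with self-harm as an item in its own right, or only as a reason for admission. A death from another cause is outside it on either parse.

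**Step 2: is an ordinary adverse event a fallback?** Section 14.1 begins "PTSD Adverse Events are defined as a" and goes on to rises in the PCL-5, the maximum PCL-5 score, and relapse into hazardous alcohol or substance use. Self-harm adverse events rest on PHQ-9 question 9 (14.1) or on failed attempts at contact (Appendix 1 item 2.4). None of these describes a death, so the 72-hour report to the investigator in 14.3 is not clearly engaged either.

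**Step 3: what does follow for an unlisted death?**

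| Route | Trigger | Time to DMEC | Investigation |
|---|---|---|---|
| 14.3; Appendix 1 items 6.1 to 6.3 | SAE | 24 hours | Yes |
| 14; Appendix 1 item 1.6 | Any participant safety issue | 48 hours after a fortnightly meeting | None stated |

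The longest delay on the second route arises if the team learns of the death just after a meeting: 14 days to the next meeting + 2 days = 16 days, against 1 day for a listed SAE. If the team learns of it just before a meeting, the delay is about 2 days.

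**Step 4: could it happen in this trial?** Section 8.3.1 sets a minimum of 20% aged 70 or over, and section 10.6 sets recruitment at 215: 0.20 × 215 = 43 people. Section 10.10.1 follows the FIRST arm to 52 weeks. A death from a cause other than suicide is a realistic event. The documents give no mortality rate, so no expected number is offered.

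**The case against.** The best counter-argument is the label. 14.2 defines PTSD SAEs, just as 14.1 sets out PTSD and self-harm adverse events as separate types, while the 24-hour duty covers all SAEs. Section 15.1 also commits the trial to the principles of GCP. On this view the psychiatric SAEs are spelled out and a wider class is taken as read. This does not close the gap, because no wider class is defined anywhere and the GCP sentence is generic. The trials unit's procedures are cited only for the DMEC's terms of reference, and the delivery partner's SAE policies only for how to investigate. It does justify saying that such a death does not *clearly* trigger the notice, rather than that the protocol forbids it.

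Several stronger readings are tempting, and the documents do not support them:

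- *The DMEC would never hear of such a death.* It would, through the safety-issue route. The loss is speed and investigation.
- *A verdict of suicide is needed before the clock starts.* No section requires cause or intent to be confirmed, and nothing stops staff from reporting a suspected suicide or suspected self-harm within 24 hours.
- *SAE counts by arm will be biased by staff who know the arm.* The protocol has unmasked roles (10.5), but it describes no step at which staff adjudicate intent and no SAE table by arm. The bias is supposition.
- *A given number of deaths will be missed.* Any such figure would rest on a mortality rate that the documents do not contain, and would also have to allow for the planned 20% loss to follow-up.

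**Conclusion.** The concern holds as a gap in the reporting rules. As written, a death of other or undetermined cause, or a life-threatening event not identified as self-harm, does not clearly attract the 24-hour notice or the SAE investigation. Its only stated path to the DMEC may take up to about 16 days and includes no investigation.

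The 16 days is a worst case. It assumes that meetings are held every 14 days, that the team learns of the event just after one, and that nobody reports early. The 43 participants aged 70 or over are the planned minimum, not a forecast. The conclusion depends on no mortality estimate, since one such death is enough to expose the gap. A careful team might well report it at once, but the protocol should not leave that to discretion. The change should be made; the point does not touch the efficacy analysis.

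**What to change.** In 14.2 and in Appendix 1 item 2.5, keep the existing list and add death from any cause and any life-threatening event, whatever the cause or intent. The 24-hour notice and the investigation in 14.3 and Appendix 1 section 6 then apply without further change to the trigger. State that cause and relatedness are classified afterwards, so that notification does not wait for them.

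While those sections are open, check who investigates. The two routes cover events during therapy and events after discharge from the delivery partner, so a waiting-list participant who has not yet started therapy has no named investigator, even for a listed SAE.

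The cost is one added phrase in two places, a sentence on later classification, and a few more 24-hour notices. No treatment, visit or analysis changes.

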14.3 Care escalation procedures

If the participant is in therapy, Inspire will hold responsibility and clinical governance accountability for the participant's mental health and wellbeing, including their own safety and where relevant the safety of others and including the safeguarding of children and vulnerable adults. If at point of referral or during the course of treatment, Inspire therapists become concerned about the welfare of any participant or immediate family member they will escalate their concerns through Inspire's standardised risk assessment, escalation, management and safeguarding policies and procedures. Where necessary they will contact the participant's GP to mobilise referral to crisis response, NHS primary or secondary care. Likewise, if a safeguarding and vulnerable adults concern is identified this will be escalated, acted on and reported to the relevant statutory body – safeguarding team.

Before the participant is referred to Inspire and after discharge, the participant's GP holds responsibility and accountability for the participant's mental health and wellbeing and this includes their safety. If the participant scores on the PCL-5 indicate an adverse event, the unmasked researcher responsible for participant safety will make contact with the participant within six hours of noting the rise in score and encourage them to contact their GP and/or case worker. They will advise the participant that they will need to contact the participants GP and/or case worker to alert them to the rise in PTSD symptoms. The research team will review all incoming follow-up PCL-5 and PHQ-9 scores within 72 hours of receipt.

All AE will be recorded and reported to the study PI within 72 hours and will be discussed at the biweekly research core-team sub-group meeting. A report will be included in the TSC reporting for review.

A Serious Adverse Event that occurs following discharge from Inspire but whilst in the trial will be investigated by one of the study's senior investigators (i.e. [name] or [name]) using Inspire's SAE investigational policies and procedures. The investigational report will be submitted to the DMEC chair.

The DMEC chair will be notified within 24 hours of the research team being notified of all serious adverse events.

All AE and SAE and the clinical and research team actions will be logged in the Trial Management File.

15 Ethics and regulatory approvals

15.1 Regulatory approvals

The trial will be conducted in compliance with the principles of the Declaration of Helsinki (1996), the principles of GCP and in accordance with all applicable regulatory requirements including but not limited to the Research Governance Framework and the Mental Capacity Act 2005.

This protocol and related documents will be submitted for review to the King's College London Research Ethics Committee.

The trial will be registered with an international registry.

The Chief Investigator will submit a final report at conclusion of the trial to the funder, the REC and the Sponsor

15.2 Confidentiality and anonymity

Each participant's personal details will be linked to a study identifier (pseudonym) and recorded in an encrypted and password protected online excel spreadsheet that three members of the research team will have access to. This file will be held on a secure KCL server. The stored therapy videos will need to show the participant's face but will be encrypted and stored using the pseudonym. We will not keep the recordings any longer than is necessary to adhere to therapy fidelity and audit requirements. Once this is confirmed the recordings will be destroyed. Participant consent will be sought for this. All data processing will be GDPR compliant and conform with standardised risk assessment, escalation, management and safeguarding policies and procedures. We are aware of the particularly sensitive nature of mental health and military veteran status in this population. These procedures were acceptable to veteran participants in our feasibility trial.

16 Success criteria and barriers to proposed work

Key success criteria are *recruiting to target* for the trial and mechanisms study (N=215). Militaryrelated memorials, domestic news items and international conflicts are highly sensitive contexts for veterans and can impact negatively on help seeking behaviours. The launching of the social medial recruitment campaign will be informed by horizon scanning for these contexts and we will work closely with PPI members and collaborator Nativve to optimise the campaign. The *delivery of therapy* at the time agreed following participant randomisation is essential to keep the commitments to transparency and trustworthiness that our PPI members have stressed upon us. A key deliverable to enable this is having twelve therapists available and with capacity. We will work closely with collaborator Inspire and trainer/supervisor [name] to manage therapist capacity and attrition.

17 Intellectual Property and Commercialisation

FIRST uses background IP developed and owned by co-applicant [name] over 15 years delivering reconsolidation and NLP interventions for PTSD. Background IP developed during the feasibility trial and RfPB grant NIHR204566, owned by KCL, will be used in the protocol. [name], through her companies Awaken Consulting and Awaken School will provide KCL with a licence for the use of her third-party background IP during the trial and for subsequent use of NHS implementation of FIRST.

18 Dissemination, outputs and anticipated impact

A report for the NIHR EME Programme will be produced and two Open Access publications to high impact journals on the trial and the mechanisms studies. NHS veteran, mental health and psychological trauma conferences will be targeted for national and international conference presentations. Dissemination plans are supported via KCL communications team's media

engagement and a trial website and Twitter account. A dissemination event will be held with invited stakeholders including, the general public, NHS managers, charity managers, therapists, veterans and their families, UK policy makers and elected Members of Parliament. The event will also be available online to increase participation across the UK.

22.1 Appendix 1: Participant safeguarding protocol

The safety of potential and actual participants is the greatest ethical concern. Our feasibility safety protocol performed well and we have strengthened it to address the safety needs of ineligible participants and participants in the Waiting List (WL) arm of the study.

This Safety Protocol follows the best practice, professional guidelines, and local NHS policies for monitoring mental state and risk throughout the participants' involvement in the trial and will be facilitated by close liaison with clinical teams. The safety of the FIRST psychotherapy intervention will be monitored closely during therapy sessions and through regular contact with the participant's clinical team or GP.

The following comprises our safety protocol for all participants in the trial: those randomised to receive the Intervention immediately, those who are placed on the WL to receive FIRST in 20 weeks' time and those that withdraw. It addresses lines of responsibility and accountability, definitions relating to safety, escalation and safeguarding procedures in the event of notable clinical deterioration with or without an escalation in risk, alongside ensuring the safe and effective management of participants who are ineligible to enter the trial.

